7.2.4 Foreseeable adverse events and anticipated adverse device effects

The following adverse events are outlined, and therefore anticipated, in the device's Instructions for Use (IFU):

Infection, increased chronic inflammation, allergic reaction, unexplained fever or chills, excessive redness, acute and chronic pain, swelling, tender scars, adhesions, seroma formation, fistula formation, hematoma, recurrence of tissue defect, anastomotic stricture formation and leaks, dyspareunia, vaginal shortening, vaginal bleeding, atypical vaginal discharge, groin and/or buttock and/or leg pain, urinary or fecal incontinence, delayed or failed incorporation of graft, failure to repair a prolapse, recurrent prolapse, mesh or suture erosion or extrusion, and injury to the bladder, bowel, blood vessels, and/or nerves of the pelvis.

7.3 Reporting Requirements

7.3.1 Reporting of AEs and SAEs

The investigator will determine if there has been a potentially device or procedure related adverse event or potentially device or procedure related serious adverse event. All potentially device or procedure related adverse events and potentially device or procedure related serious adverse events must be reported on the “Adverse Event” form.

Potentially device or procedure related adverse events and potentially device or procedure related serious adverse events will be evaluated and differentiated by:

- Seriousness of the event;
- Causality of the event (in relation to the device or procedure);

- Severity of the event.

All potentially device or procedure related AEs and potentially device or procedure related SAEs must be collected for all enrolled subjects starting from the time of enrollment through the last Follow-up. Each AE must be described as follows:

AE Term: A medically defined diagnosis/symptom. Use the highest level of evidence available.

Level 1: Diagnosis (highest level)

Level 2: Symptoms

Level 3: Signs (lower level)

AE Description: Explain the circumstance of becoming aware of the event, how the subject explained the circumstances surrounding the onset of the event, the underlying cause (the diagnosis), coexisting disease, or other condition or complaint involving the event.

AE Duration: Document by entering the date of onset (start date) and date of resolution (stop date).

AE Causality: Document causal relationship between event and the investigational product and Study Procedure (causally related, possible, probably, not related).

AE Seriousness: Document as serious or not serious.

AE Severity: Document as mild (transient and easily tolerated by the subject), moderate (discomfort and interrupts normal activities), or severe (incapacitating with inability to work or do usual activity).

Action(s) Taken and/or Treatment(s): Document as none, medication, hospitalization, surgical, and/or other. Any prescribed medication should be noted in the subject's medical records and transcribed onto the AE and Concomitant Medications CRFs. If a surgical or invasive procedure is required for an AE, document the procedure on the Invasive Procedure Log.

Outcome: Document as recovered without sequelae, recovered with sequelae, ongoing, death, or other. AEs will be followed until a resolution has occurred, until a resolution is no longer expected, the pre-existing condition returns to baseline conditions, or the subject exits the study.

7.3.2 Reporting Device Deficiency

All device deficiencies (DDs) related to the identity, quality, durability, reliability, usability, safety or performance of the study device including the analysis of used or explanted study device, where applicable, shall be documented throughout the study and managed by the sponsor.

The principal investigator shall record every observed device deficiency on the "Device Deficiency" form, together with an assessment for all enrolled subjects starting from the time of enrollment through the last Follow-up visit. Each DD must be described as follows:

Deficiency Type:

- Identity (Packaging/Labeling)
- Quality (Structure/Appearance)
- Durability (ability to withstand wear, pressure, or damage)
- Usability (use error, misuse, abnormal use)
- Reliability (Performs in a consistent manner)
- Safety (Impact on Patient Care)
- Performance (Functions according to the IFU)

When the deficiency was noted

If the deficiency was associated with an AE

If the deficiency might have led to:

- Adverse Effect
- Serious Adverse Device Effect

Device deficiencies shall be managed by the sponsor in accordance with written procedures for the control of non-conforming product. The sponsor shall take appropriate corrective and preventive actions to protect the safety of subjects, users and other persons.

In case of DD that could have led to SADE, the sponsor determines whether the risk analysis needs to be updated and assess whether corrective or preventive action is required.

The Site should make every attempt to save or collect the defective device, and if appropriate, the packaging, for return to the Sponsor. A qualified company representative will investigate and determine root cause and corrective actions as applicable, and directives will be provided to the site if warranted.

If the site documents a DD, the site will report the event in accordance with the following parameters. **It should be noted that no documents should be submitted to any regulatory**

agency without communicating with the Sponsor beforehand to assure accuracy and completeness of the information.

For DDs, the principal investigator shall:

- report to the sponsor, without unjustified delay, all serious adverse events and device deficiencies that could have led to a serious adverse device effect and documented in the AE CRFs as noted above,
- report to the IRB/EC device deficiencies that could have led to a serious adverse device effect, if required by the national regulations or by the IRB,
- report to regulatory authorities device deficiencies that could have led to a serious adverse device effect, as required by the national regulations, and
- supply the sponsor, upon sponsor's request, with any additional information related to the safety reporting of a particular event.

Device deficiencies that did not lead to an adverse event but could have led to a medical occurrence:

- a) if either suitable action had not been taken,
- b) if intervention had not been made, or
- c) if circumstances had been less fortunate,

shall be reported as specified as stated below.

Device deficiencies shall be managed by the sponsor in accordance with written procedures for the control of non-conforming product. The sponsor shall take appropriate corrective and preventive actions to protect the safety of subjects, users and other persons.

For DDs, the sponsor shall:

- report or ensure the reporting, to the IRB by the principal investigator(s), of all serious adverse events and device deficiencies that could have led to a serious adverse device effect, if required by national regulations or by the IRB,
- report to regulatory authorities, within the required time period, all serious adverse events including serious health threat and device deficiencies that could have led to a serious adverse device effect, if required by national regulations or the CIP,
- report all relevant safety information to the DMC, if established, according to written procedures.

7.3.3 Regulatory Reporting and Timelines

- **Report by the Investigator to the Sponsor**

The sponsor shall implement and maintain a system to ensure that the reporting of the reportable events as defined under Section 7.2.1 Non-Reportable Event will be provided by the investigator to the sponsor immediately, but not later than 5 calendar days after investigation site study personnel's awareness of the event.

- **Report to the IRB**

Prior to initiation of the study, reporting requirements of AEs and DDs for the IRB will be verified and documented. Reporting will occur according to the requirements set forth by the involved IRB and/or national requirements.

8 Lost to follow up

A participant will be considered lost to follow up if not able to be contacted and/or not responsive. Site will conduct a due diligence attempt per site standard operating procedures. A person search vendor approved by the Sponsor may be utilized by the site to find latest contact information for subjects on an as needed basis (Sponsor remains blinded to this activity). The site will document these proceedings for local records and complete the Sponsor's Study Completion/Exit Form.

9 Data Management

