5.1 Inclusion Criteria

1. Patient was a subject in the T-GENVIH-002 study and underwent minimally invasive (i.e., laparoscopic or robotic) surgical abdominal wall reconstruction for a primary hernia repair using Integra Gentrix® Surgical Matrix.
2. Subject has participated in the informed consent process and signed a study-specific informed consent document.
3. Subject is fluent in US English or US Spanish language.
4. Subject is willing to complete an e-consent and phone or in-office visit.

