5.5 Strategies for Recruitment

A one-off subject phone (call) visit will constitute the source of data and will be collected using a study-specific eCRF delivered via a phone script by the site responsible or their designee(s). Each patient should be included in the study only once. Patient screening will rely on site identification and contact of prior T-GENVIH-002 study subjects (Sponsor remains blinded) and e-consent process. In these cases, every effort should be made to identify every possible eligible patient. For those that are lost to follow up, site may work directly with a Sponsor approved people search service (Sponsor remains blinded). In order to be eligible for the study, patients should meet all of the eligibility criteria.

For subjects who decline an electronic consent collected remotely, an in-office interview and assistance with completing the electronic consent in person with the site study coordinator or their designee(s) will be offered for the convenience of the subjects and to maximize data collection efforts.

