6.1 Schedule of Data Collection

6.1.1 Eligibility/Consent

- The procedures to be completed are:

- ✓ Identification of the full consecutive series of patients who underwent abdominal wall reconstruction for a minimally invasive surgical approach (i.e., laparoscopic or robotic) hernia with Integra® Gentrix® Surgical Matrix from the prior T-GENVIH-002 study and informed consent for those who volunteer to participate.
- ✓ Creation on the CRF of a new case book for each eligible subject. Each created case book assigns the eligible subject with a study number.
- ✓ Completion of Worksheets/ CRFs: Site will transcribe/transmit the below-mentioned patients' data in study CRFs. The patients' data will originate from a direct interview with the subject by the study coordinator.
- The patients' data to be collected are:
 - ✓ Eligibility:
 - Inclusion Criteria: Ensure the subject meets all the inclusion criteria.

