6.1.5 Study Completion/Exit

Information will be collected by the study coordinator for each enrolled subject to reflect study exit type.

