7. ANALYSIS POPULATION

Enrolled: The enrolled population includes all eligible subjects based on the defined inclusion and exclusion criteria.

Intent-to-Treat (ITT) Population: All subjects who are enrolled into the study provide informed consent waiver and receive study intervention.

Per-Protocol (PP) Population: All subjects in the full Analysis Set not identified as major protocol violations.

The endpoints analysis will be based on the Intent-To-Treat population. The per-protocol set will be supportive and will be used to assess the robustness of study results if necessary. Safety analysis will be based on the Intent-To-Treat population.

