9.2 Study Subjects

9.2.1 Disposition of Patients

The disposition of all subjects in the study will be provided for all available data. The numbers of subjects signed informed consent waiver, screen failed, enrolled, completed, and discontinued during the study will be summarized. Disposition and reason for study discontinuation will also be provided as a by-subject listing.

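### The recurrence proportion will describe only subjects who consent and are interviewed, and the planned disposition neither starts from the full minimally invasive series nor defines a not-reached or declined category

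*Protocol*

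**What the plan says.** Protocol 6.1.1 asks the site to identify the complete consecutive set of laparoscopic and robotic cases from T-GENVIH-002 and to seek consent from those who volunteer. The next step is "Creation on the CRF of a new case book for each eligible subject". Eligibility includes consent: under Protocol 5.1, "Subject has participated in the informed consent process and signed a study-specific informed consent document". Protocol 6.1.5 then limits exit data: "Information will be collected by the study coordinator for each enrolled subject to reflect study exit type".

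On people who cannot be found, Protocol Section 8 says "A participant will be considered lost to follow up if not able to be contacted and/or not responsive", and adds "The site will document these proceedings for local records and complete the Sponsor's Study Completion/Exit Form". Protocol 5.5, on recruitment, uses the same term while the site is still looking for former subjects: "For those that are lost to follow up, site may work directly with a Sponsor approved people search service (Sponsor remains blinded".

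The primary analysis set in Protocol 10.3 (FAS) requires enrolment, consent and receipt of the study intervention. The SAP section 7 counterpart (ITT) is "All subjects who are enrolled into the study provide informed consent waiver and receive study intervention". The protocol synopsis describes the study intervention as the one-off interview. SAP 9.3 takes all endpoints from the Visit 1 questionnaire, SAP 9.3.1 reports a simple proportion, and SAP 11 rules out imputation. For disposition, SAP 9.2.1 states: "The numbers of subjects signed informed consent waiver, screen failed, enrolled, completed, and discontinued during the study will be summarized".

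**The concern.** This is a single-contact follow-up of a closed cohort. A former subject who cannot be traced, does not answer or declines never enters the analysis set. The primary result is therefore a proportion among responders, although the protocol sets out from a full consecutive series and aims to confirm continued performance over the longer term.

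Whether someone responds may be related to outcome, and in either direction. A patient whose repair failed may have gone elsewhere for care and be hard to reach; a patient with a bulge may be keener to talk. A reader of the report would need to know how many of the series were left out, and the plan does not define a count that gives this. With a planned size of about 21, each missing person carries real weight.

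There is also an operational problem. If Section 8 covers people never consented, the site is asked for an exit form for someone who has no case book or study number.

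**Working it through.** **1. Who is in the denominator.** Consent is an inclusion criterion (Protocol 5.1), so a person who declines or is not reached is not eligible. FAS/ITT also require the study intervention, which is the interview (synopsis). Endpoints come only from the Visit 1 questionnaire (SAP 9.3), without imputation (SAP 11). The recurrence proportion therefore rests on consented, interviewed subjects. This does not depend on how Section 8 is read.

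**2. What the disposition shows.** SAP 9.2.1 lists consented, screen failed, enrolled, completed and discontinued. It has no entry for the number identified under Protocol 6.1.1, and none for not located, no response or declined. Screen failure is not defined.

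**3. Section 8 against 6.1.1 and 6.1.5.**
- Subject consented, then lost before Visit 1: the case book exists and exit type is collected, so there is no conflict. This can happen, because Protocol Table 1 allows separate days.
- Former subject sought but never consented: Section 8, read with 5.5, appears to ask for an exit form, while 6.1.1 and 6.1.5 provide no record to hold it. The sections conflict.

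**4. Size.** The planned 21 (Protocol 10.2, SAP 8) has no precision target, expected rate or allowance for non-response behind it, so there is no derivation to reproduce. Neither document says whether it is the whole series or the number expected to take part. All response and recurrence counts below are assumptions.

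*If 21 is the whole series.* Let r be the number interviewed and x the recurrences among them, with no known earlier recurrence in the rest. Observed = x/r; lowest = x/21; highest = (x + 21 − r)/21. With x = 2:

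| r | Observed | Lowest | Highest |
|---|---|---|---|
| 19 | 2/19 = 10.5% | 2/21 = 9.5% | 4/21 = 19.0% |
| 17 | 2/17 = 11.8% | 2/21 = 9.5% | 6/21 = 28.6% |
| 15 | 2/15 = 13.3% | 2/21 = 9.5% | 8/21 = 38.1% |

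Each person not interviewed widens the range by 1/21 = 4.8 percentage points. With x = 0 and r = 15, the observed value is 0% and the range is 0% to 6/21 = 28.6%.

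*If 21 are interviewed from a larger series.* With x = 2, the observed value is 2/21 = 9.5%. At 10% non-participation the series is 21/0.9, rounded up to 24, and the range is 2/24 = 8.3% to 5/24 = 20.8%. At 20% it is 21/0.8, rounded up to 27, and the range is 2/27 = 7.4% to 8/27 = 29.6%.

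*Direction.* Let p be the true recurrence, and a and b the participation of those with and without recurrence. The expected observed proportion is pa/(pa + (1 − p)b). With p = 10%:
- a = 50%, b = 80%: 0.05/(0.05 + 0.72) = 6.5%.
- a = 80%, b = 50%: 0.08/(0.08 + 0.45) = 15.1%.

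**The case against.** The strongest reply is that a consented-only denominator is inherent in consent-based follow-up, and that this study is descriptive with no hypothesis to protect. The plan also works to limit non-response: every effort to identify eligible patients, a people-search service and an in-office alternative. That stands as a defence of the analysis set. It does not supply the missing counts, and a descriptive proportion needs a clear denominator as much as a tested one does.

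A reader might infer that unreached and declining subjects disappear from the disposition table altogether. The documents do not support that. Protocol Table 1 schedules case report forms at screening; with no exclusion criteria, lack of consent or unwillingness is a natural reason for screen failure; and SAP 9.2.7 would tabulate any exit form that is completed. What remains is that the category is undefined and the table does not start from the identified series.

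A reader might also take Section 8 to concern unreached former subjects and decliners outright. Its wording is participant, which also fits a consented subject lost before Visit 1. The pre-consent reading is an inference from 5.5, and decliners are not mentioned in Section 8; their exclusion follows from the consent criterion.

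Sampling error is a fair point too. At 2/15 the exact (Clopper-Pearson) 95% interval is already 1.7% to 40.5%, which contains the 9.5% to 38.1% range. But that interval assumes the responders represent the series, so it does not measure uncertainty from non-response.

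Finally, extreme bounds ignore that uninterviewed people have earlier T-GENVIH-002 data. This is correct and is carried into the fix.

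**Conclusion.** The point stands in this form: following the plan as written gives a responders-only recurrence proportion, with no defined count of the series left out and no supportive result over the whole series. Section 8 needs reconciling with 6.1.1 and 6.1.5 if it is meant to reach people who never consented. It should be corrected, though it does not invalidate a descriptive study.

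The size depends on participation, which the documents do not predict. On the assumed counts, with 21 as the whole series and no known earlier recurrence in the uninterviewed, two missing people leave a range of 9.5 points (9.5% to 19.0%) and six leave 28.6 points (9.5% to 38.1%).

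Three further inferences should be resisted. The documents do not say that follow-up will be presented as near-complete; no response or completion rate appears in them. They do not show that the proportion will be too low or too high. And SAP 11 is not restricted to enrolled subjects: it speaks of all subjects and expects missed evaluations, but only declines to impute.

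**What to change.** 1. In Protocol Section 8, state whether it covers unreached former subjects, consented subjects lost before Visit 1, or both, and align 6.1.1 and 6.1.5 with that choice.
2. Have the site supply aggregate, de-identified counts for the whole minimally invasive series: identified, not located, no response, declined, deceased, consented, interviewed. Start the SAP 9.2.1 disposition from the identified total, and define screen failure. Aggregate counts are preferable to individual rows for non-consenting people, because Protocol 5.4 ties use of data to consent and the sponsor stays blinded to the search.
3. In SAP 9.3.1, label the FAS/ITT proportion as responders-only. Add a supportive result over the full series with lowest and highest possible values, counting recurrences already recorded in T-GENVIH-002 for subjects not interviewed where use of those data is permitted.
4. In Protocol 10.2 and SAP 8, state whether 21 is the series size or the expected number interviewed.

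The cost is small. The site must already identify the series and document its searches, so this adds a set of counts, some disposition rows and one supportive line, with no new patient contact. Minor IRB wording may be needed, and the reported follow-up will look less complete.

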9.1 Methods for data collection and data entry

An EDC system which is a 21 CFR Part 11-compliant data capture system with eCRF designed and the study database built will be used for the purposes of this clinical investigation. The data entered into the EDC system will be reviewed and cleaned. Queries will be issued to the site via the EDC system and are to be resolved by the investigator or his designee using the EDC system. An audit trail in the system is available for tracking all information including the site user enters, modifies, or deletes the study data and query resolution.

Data review and data cleaning will be completed on a regular basis. The study data will be reviewed and cleaned to ensure that there are no outstanding data discrepancies prior to database lock. Any changes to the database after that time will require written agreement by Integra LifeSciences Corporation.

A Data Management Plan is prepared to document precisely the procedures for the study database development, data review, data cleaning and query resolution.

9.2 Source Data Requirements

Data collection is the responsibility of the clinical trial staff at the site under the supervision of the site investigator. The investigator is responsible for ensuring the accuracy, completeness, legibility, and timeliness of the data reported.

The investigator or its delegate will perform primary data collection drawn directly from the subject by use of an interview (either by phone or in-person) by the study coordinator, using a paper Case Report Form that the coordinator will fill out. Source data is defined as all information in original records, certified copies of original records of clinical findings, observations, or other activities in a clinical investigation, necessary for the reconstruction and evaluation of the clinical investigation. All source documents should be completed in a neat, legible manner to ensure accurate interpretation of data. In this study, the Case Report Form is a Source Document.

Clinical data (including adverse events (AEs) will be entered into EDC system, a 21 CFR Part 11-compliant data capture system, provided by the Sponsor. The data system includes password protection and internal quality checks, such as automatic range checks, to identify data that appear inconsistent, incomplete, or inaccurate. Clinical data will be entered directly from the source documents.

The investigator shall ensure the accuracy, completeness, legibility, and timelines of the data reported in CRF and in all required documentation. Data reported on the CRF shall be supported by the source documents with any discrepancies being explained. Any corrections made to documents will be done according to ISO 14155 guidelines. If an item is not available or is not applicable, this fact should be indicated; no space is to be left blank. The investigator who has signed the clinical investigation plan signature page or his/her authorized designee is to personally sign the CRFs to validate that the observations and findings are recorded on the eCRFs correctly and completely. The CRFs are to be completed in a timely manner after the subject's visit. Failure to meet the documentation requirements may lead to the disqualification of an investigator.

